**Date of Document: January 27th, 2021**

**Study design:** experimental study, non-pharmacological trial

## **Background**

Adequate calcium supplementation in association with the Mediterranean diet and lifestyle physically active can improve the quality and even life expectancy in the population, with a reduced risk of osteoporosis. Mineral water can be a good source of calcium,

highly bioavailable and easily assimilated. Calcium is naturally abundant in waters minerals that represent precious non-caloric sources. Mineral waters, assumed daily, with a high calcium content (over 150 mg/L) and a low sodium content

(less than 20 mg/L) can be considered excellent sources of this mineral.

Until a few years ago, calcium from water was believed to be poorly absorbable compared to that contained in other food sources, but several scientific studies have reversed this conviction, especially for calcium (calcium > 150 mg/L) and bicarbonate- calcium waters (bicarbonate > 600 mg/L). Furthermore, several studies have shown that the effects of sodium on the organism they are many and would also concern the bones, so much so that its effect hypercalciuric in the urine has led to hypothesize a possible role of sodium in the pathogenesis of osteoporosis. Bicarbonates make water alkaline and affect water markers bone resorption. In this scenario, the daily consumption of bicarbonate-calcium waters with a low sodium content is a major contributor to calcium intake and a significant protective factor for osteoporosis.

## **Objective**

Evaluate the effectiveness of regular consumption of Lete water classified as bicarbonate-calcium e low sodium for the prevention of osteoporosis in premenopausal and postmenopausal women as part of a defined dietary protocol.

## **Materials**

Subjects enrolled in the study:

120 women

Inclusion Criteria:

For premenopausal women age >40 years, for menopausal women period of onset of menopause 1-10 years, with BMI of 19-30 Kg/m^2.

Exclusion criteria:

Inclusion in other study protocols. Pharmacological therapies in progress: estrogen hormone therapy replacement, osteoporosis therapy, corticosteroid therapy, insulin therapy.

Assumption of

calcium supplements. Presence of moderate to severe kidney and liver disease, already documented severe osteoporosis condition (T-score MOC  $<-2.5$ ).

Waters:

- Lete bicarbonate-calcium water, low in sodium
- non-bicarbonate-calcium water: the ideal comparison water is low-mineral water from bottled with the same packaging as that of Lete water, with the addition of CO2.

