## Methods

The subjects enrolled for the study will be divided into two main groups: premenopause A and postmenopausal B and then subsequently randomly in the two subgroups and respectively

- Group A1 (intervention group): 30 premenopausal subjects who will drink water  
The bicarbonate-calcium Lete

- Group A2 (control group): 30 premenopausal subjects who will drink water  
low mineral content

- Group B1 (intervention group): 30 postmenopausal subjects who will drink water  
The bicarbonate-calcium Lete

- Group B2 (control group): 30 postmenopausal subjects who will drink water

low mineral content

The study will be randomized single-blind.

As for the water to be taken, the bottles will be delivered at the expense of the company SGAM SpA in the following ways: the entire study takes a total of 6 months

considering that the recruited subjects (120) must drink 2 L of water per day 43200 L of water, of which 21600 L Lethe bicarbonate-calcium water and 21600 L mineral water with added CO2. For each subject, 240 1.5 L bottles are needed. As regards logistics,

the subjects they will receive home delivery of the assigned water and precisely 10 packs of 6 bottles each for a total of 4 deliveries at set times.

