### **Study**

Study of the ability to assimilate calcium by drinking bicarbonate water with a high calcium and low sodium vs control (low mineral water) in women in pre

and postmenopausal for a period of 6 months. After the end of the study there will be a period of follow-up for study monitoring.

Subjects will follow a Mediterranean diet of 25-30 kcal/kg of ideal bodyweight/day (possibly free from acidic foods, controlling calcium intake <700 mg/day, of 1 g/weight ideal protein per day, carbohydrates with a low glycemic index 60%, lipids mainly of type unsaturated 40%). The effects of water intake will be evaluated in relation to the presence of bicarbonates also on the functionality of the digestive and locomotor systems. During recruitment subjects will complete a FFQ Food Frequency Questionnaire to establish their daily intake of calcium in the diet.

The patients will be recruited by the associations Amos Paternopoli, Amos Montoro, Amos Forino, Amos Solofra, Noi in Rosa, Amos Valle del Sabato.

The study includes measurements at 0, 3 and 6 months. Operational center of the study: Research Laboratory University nutrition Nutri keto\_Lab, "San Giuseppe Moscati" Hospital of Avellino.

The two groups will be subjected to the indicated study protocol and will carry out:

- Recruitment test C (clinical, anthropometric, instrumental and blood chemistry tests)
- Test I after set times (Mediterranean diet, with 2 L Lete water (30 women in group A1 and in group B1) or with 2 L mineral water (30 women in group A2 and in that B2), with 500 mL with meals three times a day and the remainder during the day.

The following tests will be performed:

Clinical examinations: Physiological and pathological history, physical examination and nutritional

evaluation,

to investigate the patient's clinical conditions and the functionality of the digestive and locomotive systems

Instrumental examinations: computerized bone mineralometry (MOC), articular ultrasound to evaluate the degree of elasticity, BIA/BIVA for the qualitative and quantitative evaluation of the body composition;

Metabolomic analysis of serum, urine, and saliva samples by spectroscopy nuclear magnetic resonance to investigate change in glyceemic, lipidic and bone metabolism.

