### **Processing of results**

Statistical analysis, data visualization and predictive analysis will be carried out through Statgraphics software (Statgraphics Technologies, Inc., The Plains, Virginia). Features of the population included in the study will be analyzed by descriptive techniques. In

all evaluations made the results will be expressed as arithmetic mean and deviation

standard. The statistical analysis of the parametric data will be performed with the Student's T test for measurements paired and unpaired, comparing data at the start and at the end and then between the control and the intervention group. P-values  $<0.05$  will be considered statistically significant.

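### A T-score below -2.5 excludes a woman only if it was already documented, although the trial measures it at time 0 and no rule links that result to eligibility or randomisation

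*Protocol*

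**What the plan says.** **Entry rule (Protocol, Materials).** The exclusion list reads "Presence of moderate to severe kidney and liver disease, already documented severe osteoporosis condition", followed in brackets by the cut-off, a MOC T-score below -2.5. The kidney and liver part depends on presence. The osteoporosis part depends on earlier documentation. The same list bars women taking calcium supplements and those with "Pharmacological therapies in progress: estrogen hormone therapy replacement, osteoporosis therapy, corticosteroid therapy, insulin therapy".

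**Measurement (Protocol, Study, and the MOC line at the end of the protocol).** Participants undergo "Recruitment test C (clinical, anthropometric, instrumental and blood chemistry tests"), and MOC is listed among the instrumental examinations. The closing line of the protocol schedules MOC in 120 patients at time 0 and at 6 months.

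**Order of steps (Protocol, Methods and Study).** Methods says "The subjects enrolled for the study will be divided into two main groups", by menopausal status, and that random allocation to the two waters follows. Study then says "The two groups will be subjected to the indicated study protocol and will carry out" the recruitment test and the later test. Neither section says whether the time-0 MOC is read before allocation.

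**Setting.** The objective is prevention of osteoporosis. The diet includes "controlling calcium intake <700 mg/day" for 6 months, and two of the four groups of 30 drink low-mineral water.

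The SAP covers the sample size for CTX and says nothing on eligibility.

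**The concern.** The protocol has already decided that a woman with a T-score below -2.5 does not belong in this trial. It then makes that decision depend on whether someone recorded the value beforehand, although the trial will measure it in every woman. Two women with the same T-score are treated differently according to whether they happened to have an earlier scan.

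The first issue is participant protection. At time 0 the study staff would hold a result below the protocol's own cut-off with no instruction to act on it. The woman enters without osteoporosis therapy or calcium supplements, because women using either are excluded. She follows the controlled-calcium diet and may be assigned the low-mineral water.

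The second issue is fit with the objective. A woman already below the cut-off is not a candidate for prevention. If centre staff resolve the ambiguity case by case, the enrolled population is not the one that the criteria describe.

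**Working it through.** The plan gives no figure on this point to reproduce. The check is a reading of the rule against the schedule, followed by the cost of closing the gap.

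**1. Apply the rule as written.**

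| Woman | T-score | Known before the trial? | Excluded by the text? |
|---|---|---|---|
| A | below -2.5 | yes | yes |
| B | below -2.5 | no, first seen at the time-0 MOC | not stated; literally, no |
| C | -2.5 or above | either | no |

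Only woman B is in question. The time-0 MOC will identify her, and no sentence says what happens next.

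**2. Does the order of steps settle it?** No.
- The name of the recruitment test suggests that it precedes enrolment, which favours a screen.
- The phrase "The two groups will be subjected to the indicated study protocol and will carry out" suggests that the groups already exist when the test is done. But Methods uses two main groups for the menopausal strata, which are formed before randomisation, so this wording is compatible with either order.
- MOC is planned in 120 patients, and 4 × 30 = 120, so there is no surplus for women who fail the test. But 120 is used as a target throughout. The water budget uses it too: 120 women × 2 L × 180 days = 43,200 L, with no allowance for attrition. The figure does not show the order of testing.

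The documents therefore neither confirm nor rule out a screen.

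**3. Cost of screening.** The documents give no rate of first-found T-scores below -2.5. I assume 2-10% of postmenopausal women for illustration. To keep 60 postmenopausal women (30 + 30):
- at 2%: 60 / 0.98 = 61.2, so 62 screened, 2 extra;
- at 10%: 60 / 0.90 = 66.7, so 67 screened, 7 extra.

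These are averages. At 10%, screening 67 women yields at least 60 eligible with probability 0.65 (binomial, 67 trials, success probability 0.90), so recruitment should continue until the groups are full. Premenopausal women who fail would add to these numbers.

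**4. Sample size.** The SAP's 28 per group (30 planned) depends on the CTX difference, its standard deviation, alpha and power. The eligibility wording enters none of these, and excluded women are replaced, so the figure is unaffected.

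**The case against.** The strongest reply is that the natural sequence is recruitment test, enrolment, randomisation. On that reading a low T-score found at recruitment is documented by the time of allocation, and the criterion works. The text also reads as a loose translation, so two words should not carry too much weight. This reading is plausible, and the count of 120 does not refute it. But it is nowhere written, and two staff members could handle the same woman differently. If a screen is intended, the rewording only records it.

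Other objections stand, and they limit the point:
- **Number affected.** The 2-10% is an assumption with no source in the documents. It illustrates cost and is not an estimate of how many women would be wrongly enrolled.
- **Calcium contrast.** A reader might multiply the Background's figure of over 150 mg/L by 2 L and infer that controls forgo more than 300 mg/day. The documents give neither Lete's calcium content nor the comparison water's, so they do not support that figure. Nor do they show that the diet lowers anyone's intake, since habitual intake is still to be measured by questionnaire.
- **Treatment.** The criteria bar osteoporosis therapy in progress at entry. Nothing bars treatment started later.

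**Conclusion.** The point holds as a gap in a stated rule. The protocol sets a T-score cut-off, measures the T-score at time 0, and does not connect the two. Read literally, a newly found case can be randomised. The documents do not show that this will happen, because the recruitment test may be intended as a screen. The number of women concerned cannot be derived, but the gap exists at any rate above zero. The CTX comparison is not called into question.

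A reader might infer two wider failures, and the documents do not support treating them as part of this error:
- **Kidney disease.** Moderate to severe disease is excluded by its presence, so a new case is already covered. A creatinine-clearance cut-off and a named reader would be useful detail, but the stated rule has no hole.
- **Adverse events.** No standard adverse-event question or count by arm is set out. But Study plans history and examination "to investigate the patient's clinical conditions and the functionality of the digestive and locomotive systems", and the laboratory panel is repeated at 0, 3 and 6 months in all women. The statement that in "all evaluations made the results will be expressed as arithmetic mean and deviation" (standard deviation) describes how results are summarised and does not rule out a count of events. A fixed question at months 3 and 6, and a doctor's reading of the later panels, are optional additions.

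**What to change.** 1. Reword the exclusion criterion in Materials to: *T-score MOC < -2.5, already documented or found at the time-0 MOC*.
2. State in Methods that the study doctor reads the time-0 MOC before randomisation.
3. State that a woman who meets the criterion is referred for care, is not randomised, and is replaced so that each group still reaches 30.

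**Cost.** The MOC is already scheduled for every woman who enters, so the only new scans are those of the replacements. Randomisation has to wait for the result. The number of extra women screened is unknown: about 2-7 postmenopausal women on average under the assumed 2-10%, each needing one more time-0 assessment, plus any premenopausal women who fail. No change to the sample size or the CTX analysis is needed.

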## Methods

The subjects enrolled for the study will be divided into two main groups: premenopause A and postmenopausal B and then subsequently randomly in the two subgroups and respectively

- Group A1 (intervention group): 30 premenopausal subjects who will drink water  
The bicarbonate-calcium Lete

- Group A2 (control group): 30 premenopausal subjects who will drink water  
low mineral content

- Group B1 (intervention group): 30 postmenopausal subjects who will drink water  
The bicarbonate-calcium Lete

- Group B2 (control group): 30 postmenopausal subjects who will drink water

low mineral content

The study will be randomized single-blind.

As for the water to be taken, the bottles will be delivered at the expense of the company SGAM SpA in the following ways: the entire study takes a total of 6 months

considering that the recruited subjects (120) must drink 2 L of water per day 43200 L of water, of which 21600 L Lethe bicarbonate-calcium water and 21600 L mineral water with added CO2. For each subject, 240 1.5 L bottles are needed. As regards logistics,

the subjects they will receive home delivery of the assigned water and precisely 10 packs of 6 bottles each for a total of 4 deliveries at set times.

### **Sample size**

An analysis was performed to calculate the sample size and evaluate the power of the clinical trial statistics. The power of the (1-beta) test to be obtained, i.e., was considered as factors the probability of rejecting the null hypothesis when there is a real difference, the least difference between the treatments (control and intervention group), the variability of the measure and finally the level of significance  $\alpha$  (5%), i.e. the probability of obtaining a statistically significant difference when in fact there is no difference. A priori information from the literature was used scientifically.

### **Study**

Study of the ability to assimilate calcium by drinking bicarbonate water with a high calcium and low sodium vs control (low mineral water) in women in pre

and postmenopausal for a period of 6 months. After the end of the study there will be a period of follow-up for study monitoring.

Subjects will follow a Mediterranean diet of 25-30 kcal/kg of ideal bodyweight/day (possibly free from acidic foods, controlling calcium intake <700 mg/day, of 1 g/weight ideal protein per day, carbohydrates with a low glycemic index 60%, lipids mainly of type unsaturated 40%). The effects of water intake will be evaluated in relation to the presence of bicarbonates also on the functionality of the digestive and locomotor systems. During recruitment subjects will complete a FFQ Food Frequency Questionnaire to establish their daily intake of calcium in the diet.

The patients will be recruited by the associations Amos Paternopoli, Amos Montoro, Amos Forino, Amos Solofra, Noi in Rosa, Amos Valle del Sabato.

The study includes measurements at 0, 3 and 6 months. Operational center of the study: Research Laboratory University nutrition Nutri keto\_Lab, "San Giuseppe Moscati" Hospital of Avellino.

The two groups will be subjected to the indicated study protocol and will carry out:

- Recruitment test C (clinical, anthropometric, instrumental and blood chemistry tests)
- Test I after set times (Mediterranean diet, with 2 L Lete water (30 women in group A1 and in group B1) or with 2 L mineral water (30 women in group A2 and in that B2), with 500 mL with meals three times a day and the remainder during the day.

The following tests will be performed:

Clinical examinations: Physiological and pathological history, physical examination and nutritional

evaluation,

to investigate the patient's clinical conditions and the functionality of the digestive and locomotive systems

Instrumental examinations: computerized bone mineralometry (MOC), articular ultrasound to evaluate the degree of elasticity, BIA/BIVA for the qualitative and quantitative evaluation of the body composition;

Metabolomic analysis of serum, urine, and saliva samples by spectroscopy nuclear magnetic resonance to investigate change in glyceemic, lipidic and bone metabolism.

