**STATISTICAL
ANALYSIS PLAN**

Official title: Evaluation of the effects of taking bicarbonate-calcium water in premenopausal and postmenopausal women as prevention of osteoporosis

Date of Document: January 27th, 2021

Data from scientific literature were used to calculate the sample size and evaluate the power of the clinical study, and in particular: • Meunier, PJ, Jenvrin, C., Munoz, F., de la Gueronniere, V., Garnero, P., & Menz, M. (2005).

Consumption of a high calcium mineral water lowers biochemical indices of bone remodeling in postmenopausal women with low calcium intake. *Osteoporosis international*, 16(10), 1203-1209

As a reference for the statistical calculations, a biochemical parameter was considered, which represents a primary endpoint of the study, the value of CTX (C-terminal telopeptide of type I collagen), a serum marker of bone turnover.

Both of the studies cited analyzed the effects of calcium-rich bicarbonate alkaline water in samples of women: in the first case in menopausal women and in the second in women in the 18-45 age range.

The results of the two studies are reported in the summary table.

Meunier et al., 2005		
S. CTX (pmol/L)	Control group (n=43) 2	Intervention group (n=44)
baseline	0.503±0.039	0.542±0.032
month 6	0.591±0.037	0.449±0.034
Wynn et al., 2009		
S. CTX (g/L)	Control group (n=15)	Intervention group (n=15)
baseline	0.380±0.115	0.479±0.261
weeks 4	0.389±0.110	0.401±0.234

Predictive statistical analysis was determined using Statgraphics software (Statgraphics Technologies, Inc., The Plains, Virginia).

Below are the results.

The power of the test (1- β) to be obtained (95%) was considered as factors for the calculation of the sample size, i.e. the probability of rejecting the null hypothesis when there is a real difference, the minimum difference between the treatments (control and intervention group), the variability of the measure and finally the level of significance α (5%), i.e. the probability of obtaining a statistically significant difference when in fact there is no difference.

First analysis (Meunier et al., 2005)

Sample-Size Determination

Parameter to be estimated: difference between two normal means

Desired power: 95,0% for difference = 0,142 versus difference = 0,176

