Type of alternative: not equal

Alpha risk: 5,0%

[figure not shown]
Sigma: 0,034 (to be estimated)

The required sample size is 28 observations from sample 1 and 28 observations from sample 2.

The StatAdvisor

This procedure determines the sample size required when comparing the means of two normal distributions. Assuming that the standard deviations of the normal distributions equal 0,034, 28 observations are required in sample 1 and 28 in sample 2 to have a 95,0% chance of rejecting the hypothesis that $\mu_1 - \mu_2 = 0,142$ when the true $\mu_1 - \mu_2 = 0,176$ (using a two-sided test).

The result estimates that 28 subjects are needed for each group to be enrolled (control and intervention group), in order to ensure a statistical power of 0.95 with an $\alpha = 0.05$, using a two-tailed t-test.

For our study we assumed to recruit 30 subjects for each group (the results of the statistical analysis suggest 28 subjects for each group). Therefore, always using these available data in terms of mean, standard deviation and difference between treatments, we evaluate the power of the study at 95% confidence.

Parameter to be estimated: difference between two normal means

Sample sizes: 30 and 30

[figure not shown]
Confidence level: 95,0%

Sigma: 0,034 (to be estimated)

The tolerance for the difference will be +- 0,0175726

The StatAdvisor

This procedure determines the sample size required when comparing the means of two normal distributions. Assuming that the standard deviations of the normal distributions equal 0,034, 30 observations in the first sample and 30 in the second sample will estimate the true $\mu_1 - \mu_2$ to within $\pm 0,0175726$ with 95,0% confidence.

Second analysis (Wynn et al., 2009)

The same procedure is repeated using the data of the second scientific article cited.

Sample-Size Determination

Parameter to be estimated: difference between two normal means

Desired power: 95,0% for difference = 0,012 versus difference = 0,246

Type of alternative: not equal

[figure not shown]
Alpha risk: 5,0%

Sigma: 0,234 (to be estimated)

The required sample size is **28** observations from sample 1 and **28** observations from sample 2.

The StatAdvisor

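### The only inference rule, unadjusted t tests at p<0.05, applies by default to NMR metabolite profiles of three body fluids, so chance significant findings are likely and nothing labels them exploratory

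*Protocol*

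**What the plan says.** Among the tests listed in the Protocol under Study is "Metabolomic analysis of serum, urine, and saliva samples by spectroscopy nuclear magnetic resonance", intended to show changes in glycaemic, lipid and bone metabolism. The text does not give the number of metabolites or spectral bins, or how a spectrum becomes variables for analysis.

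The inference rule stands in the Protocol under Processing of results: "The statistical analysis of the parametric data will be performed with the Student's T test for measurements paired and unpaired". The paired tests set final values against baseline within a group; the unpaired tests set one arm against the other. P-values below 0.05 "will be considered statistically significant". The section contains no adjustment for the number of tests, no ranking of outcomes and no separate method for the metabolomic data. It does mention predictive analysis, without defining it.

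The SAP does not mention metabolomics. It contains only sample-size work for serum CTX, which it names as a primary endpoint. Under Methods, the Protocol randomises 30 versus 30 within the premenopausal group and 30 versus 30 within the postmenopausal group. It does not say whether the two strata are analysed together or apart.

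**The concern.** A 5% threshold limits the error of one test. A metabolite profile is a screen of many variables, here repeated in three fluids and possibly in two strata. If each variable is judged on its own at 0.05, the expected number of chance findings grows in proportion to the number tested. Nothing in the plan would tell a reader that such a finding came from a screen, how many variables were screened, or that it carries less weight than the CTX result. The risk is that a list of metabolites is presented as changed by the water when the list is about as long as chance alone would produce.

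Adjusting CTX, bone density and the listed laboratory tests for multiplicity would not settle this, because the metabolites are a separate and open-ended set of tests.

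**Working it through.** **1. The plan's own figure.** The SAP's first calculation uses a two-sided alpha of 5% ("Type of alternative: not equal"), "Desired power: 95,0% for difference = 0,142 versus difference = 0,176", and an SD of 0.034. The difference to be detected is 0.176 - 0.142 = 0.034, which is one SD.

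- Normal approximation: n = 2 × (1.960 + 1.645)² × (0.034/0.034)² = 25.99, so 26 per group.
- Noncentral t: 27 per group; the SAP states 28.
- For 80, 85 and 90% power the noncentral t gives 17, 19 and 23, as stated.
- Tolerance at 30 per group: t(0.975, 58 df) × 0.034 × √(2/30) = 0.0175726, as stated.

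The calculation reproduces to within one or two subjects. It concerns one variable tested once, and gives no protection to the metabolite tests.

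**2. Expected chance findings.** Let m be the number of metabolites per fluid (assumed; not in the documents). With three fluids and c between-arm comparisons per metabolite, the number of tests is K = 3 × m × c. With no difference between the waters, the expected number of false findings is 0.05 × K, whatever the correlation.

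| m per fluid | Strata pooled (c = 1): K, expected | Strata separate (c = 2): K, expected |
|---|---|---|
| 10 | 30, 1.5 | 60, 3 |
| 20 | 60, 3 | 120, 6 |
| 50 | 150, 7.5 | 300, 15 |

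The rule also orders paired start-to-end tests. Run in all four subgroups, they bring the total to 6 tests per metabolite. If nothing changed over time either, the expected counts would be 0.05 × 3 × m × 6 = 9, 18 and 45. These totals are less firm as counts of false findings, because all women start the study diet and a within-group change may be real without being due to the water.

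**3. Chance of at least one false finding.** For independent tests this is 1 - 0.95^K: 78.5% at K = 30, 95.4% at K = 60 and 99.8% at K = 120.

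Metabolites are correlated, so this was simulated for 120 variables in 30 versus 30 women with no true difference and a common correlation (3,000 runs each):

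| Correlation | Mean false findings | Chance of at least one | 5th-95th percentile |
|---|---|---|---|
| 0 | 6.0 | 99.8% | 2-10 |
| 0.3 | 5.9 | 96.5% | 1-18 |
| 0.6 | 6.2 | 69.3% | 0-31 |

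A separate simulation gave about 96% at correlation 0.3 and 68% at 0.6. Correlation leaves the mean at about 6, lowers the chance of any false finding and widens the spread: some trials would show none, others a cluster of dozens.

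**4. Effect of the remedy.** In the same simulated data, Benjamini-Hochberg at 5% over all 120 tests gave at least one false finding in 4.7, 4.3 and 2.9% of trials at correlation 0, 0.3 and 0.6. Applied within each fluid instead, with independent fluids and no true effect, the chance of any false claim is about 1 - 0.95³ = 14%. That is the reason for one family across fluids.

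**The case against.** The strongest objection is that neither document says each metabolite gets a t test. The rule is worded for parametric data, and the same section names predictive analysis, so a multivariate method may have been intended. This stands as a limit: per-metabolite testing is inferred from the absence of any other rule. It does not remove the point. The SAP uses almost the same term for its sample-size calculation, and if another method is meant, it is not written down.

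The size also rests on assumptions. A small targeted set is possible, since the Protocol directs the analysis to three areas of metabolism; at 10 per fluid with strata pooled, the expected count is only 1.5. Separate testing of the strata is likewise assumed.

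CTX is already set apart, in that the SAP names it as a primary endpoint and sizes the trial on it. That is fair, but no text places the metabolomic results below it.

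A reader might infer more: that the metabolomic part could never come out negative, or that a benefit would be reported even for two identical waters. The documents do not support either. At correlation 0.6 about 31% of null trials in the simulation showed no finding (100 - 69.3). With two-sided tests, chance findings fall in either direction, and nowhere is a single metabolite below 0.05 said to count as a benefit.

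Finally, a false-discovery rate is one reasonable choice; family-wise control would also limit chance claims, at a stricter threshold (Bonferroni at 120 tests: 0.05/120 = 0.00042).

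**Conclusion.** The point holds in a limited form. As written, an unadjusted 5% rule applies by default to a three-fluid metabolite profile that has no exploratory label. Under no effect, the expected number of chance findings runs from 1.5 (10 metabolites per fluid, strata pooled) to 15 (50 per fluid, strata separate), before any paired tests. At least one is likely but not certain: about 68 to 99.8% with 120 tests, depending on correlation.

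This rests on the assumed metabolite counts, on the default rule being the one applied, and on a simulation with equal correlation between all metabolites. It does not touch the CTX comparison or its sample size. It is a cheap improvement, not a flaw that puts the trial's main result in doubt.

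**What to change.** Add to Processing of results in the Protocol, and carry into the SAP, text to this effect:

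> Metabolomic results are exploratory. Between-arm tests of metabolites are controlled by the Benjamini-Hochberg procedure at a 5% false-discovery rate, in one family across serum, urine and saliva, and across both menopausal strata if these are tested separately. The number of metabolites tested and the q-values are reported. A metabolite with only an unadjusted p below 0.05 is not called significant.

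The same text should say whether the strata are pooled.

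No sample, visit or assay changes; the work is wording and a standard adjustment. The cost is that fewer metabolites will be called significant. As a bound, take 20 per fluid in both strata, so 120 tests of 30 versus 30. A true difference of one SD has 96.8% power at 0.05 and 55.4% at the Bonferroni threshold of 0.00042. Benjamini-Hochberg lies between the two, because it rejects everything Bonferroni rejects and nothing above 0.05. For a screen labelled exploratory, that is a fair price.
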